## **7.2      Laboratory Evaluations**

### **7.2.1      Clinical Laboratory Evaluations**

At the screening visit, V0, diagnostic laboratory tests for determination of *C. trachomatis*, *N. gonorrhoeae*, and *T. vaginalis* (NAATs) will be performed locally. Vaginal Gram stain Nugent scoring for microbiologic confirmation of clinical findings will be conducted in the Central Laboratory. BD Max baseline testing will be conducted at a certified laboratory. Instructions for obtaining vaginal swab specimens for these assessments are outlined in the protocol-specific MOP.

A urine pregnancy test will be performed at all visits on all participants of childbearing potential. Screening and enrollment visit results must be negative and known prior to randomization on V1.

---

At all scheduled study visits a BD Max test will be conducted at a certified laboratory. At the enrollment and follow-up visits, vaginal Gram stain Nugent scoring for microbiologic confirmation of clinical findings will be conducted in the Central Laboratory. At the follow-up visits participants with clinically diagnosed VVC will have a confirmatory culture for vaginal *Candida* with speciation performed locally.

#### **Nugent Criteria for Determination of BV:**

A vaginal swab for microbiologic assessment of BV by Nugent criteria should be performed. The Nugent score utilizes a 0-10 point scale for evaluation of vaginal flora and is based on the weighted sum score of the following three bacterial morphotypes calculated from the slide exam under oil immersion (1000x):

- *Lactobacillus*: Large Gram-negative rods
- *Gardnerella/Bacteroides* spp: thin, curved, Gram-variable rods
- *Mobiluncus* spp: thin, curved, Gram-variable rods

The Nugent score is interpreted as follows: 0-3 normal; 4-6 intermediate; and 7-10 BV. For the purposes of this study, a Nugent score of  $\geq 7$  will be used to define a microbiologic recurrence of BV for ancillary analysis.

#### **Candida Culture for Determination of VVC:**

For participants with a clinical diagnosis of VVC at V1-V4, a vaginal swab should also be taken for confirmation of *Candida* by culture with speciation. See the protocol-specific MOP for further details.

##### **7.2.1.1 Laboratory Specimen Preparation, Handling, and Storage**

Specimen preparation, handling, and storage will be done according to local clinic SOPs. The enrolled participants study specimens collected for the BD Max testing and gram stain slides will be stored until the end of the study and then destroyed. Likewise, for enrolled participants, the additional vaginal swab collection and non-albicans *Candida* strain cultures only will be stored for future use. Additional details can be found in the protocol-specific MOP.

---

### **7.2.1.2    Laboratory Specimen Shipping**

Gram stain and BD Max specimen shipment to the Central Laboratory will occur according to all applicable International Air Transport Association (IATA) requirements. The Central Laboratory address is as follows:

## 8 ASSESSMENT OF SAFETY

### 8.1 Assessing and Recording Safety Parameters

Safety will be monitored throughout the study by targeted physical and pelvic examination; and participant reporting. Safety will be assessed by the frequency and severity of:

1. Serious AEs occurring after randomization and from the time of the IP dose through V4.
2. Non-serious AEs occurring after randomization and from the time of the IP dose through V4.

#### 8.1.1 Adverse Events (AEs)

ICH E6 defines an AE as any untoward medical occurrence in a participant or clinical investigation participant administered a pharmaceutical product regardless of its causal relationship to the study treatment. An AE can therefore be any unfavorable and unintended sign (including an abnormal laboratory finding), symptom, or disease temporally associated with the use of medicinal (investigational) product. The occurrence of an AE may come to the attention of study personnel during study visits and interviews of a study participant presenting for medical care, or upon review by a study monitor.

All AEs not meeting the criteria for “serious adverse events” should be captured on the appropriated CRF. Information to be collected for AEs includes event description, date of onset, clinician’s assessment of severity, relationship to IP (assessed only by those with the training and authority to make a diagnosis, or his/her designee), date of resolution/stabilization of the event. All AEs occurring while on study must be documented appropriately regardless of relationship. All AEs will be followed to adequate resolution.

Any medical condition that is present at the time that the participant is screened will be considered as baseline and not reported as an AE. However, if it deteriorates at any time during the study, it should be recorded as an AE.

All AEs must be graded for severity and relationship to IP.

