### **2.3.1.1 Potential Risks Associated with TOL-463**

The safety and tolerability of TOL-463 are supported by the results of completed Phase I and Phase II clinical studies sponsored by the NIH through the NIAID, Division of Microbiology and Infectious Diseases (DMID Protocol No. 11-0077 and 15-0039, respectively). The findings are consistent with the two-week Good Laboratory Practice (GLP) vaginal irritation and toxicity study of TOL-463 with toxicokinetic endpoints in rabbits, also sponsored by the NIH, demonstrating absence of safety signals and minimal systemic exposure to TOL-463. The most common treatment-related adverse events, (AEs), reported in TOL-463 clinical trials were localized in nature, e.g., vulvovaginal burning and pruritus, and none led to discontinuation of study product. All treatment-related AEs were mild to moderate in intensity and self-limiting. No serious or severe AEs related to TOL-463 were reported. Please refer to Investigator's Brochure (IB) for additional information.

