### 5.1.1.1 Screening Visit(s) Inclusion Criteria:

1. Women with a current BV infection and a history of at least two previous episodes of BV by documentation or self-report in the past year. V0 diagnosis is based on the presence of  $\geq 3$  Amsel criteria\*;

\*Homogeneous vaginal discharge; positive KOH whiff test; vaginal pH of  $> 4.5$ ; and  $\geq 20\%$  clue cells.

2. Willing and able to provide written informed consent;
3. Age 18-55 years of age at the time of V0;
4. General good health based on medical history, targeted physical examination, and pelvic examination;
5. For participants 21 years of age or older, Pap test performed within the past 3 years, with the most recent result being normal or ASCUS HPV negative OR Pap smear collected at V0\*;

\*Consistent with current Pap screening guidelines, a Pap smear must be performed at V0, for women who meet the following criteria and cannot provide documentation or self-report of a normal or ASCUS HPV negative Pap smear, conducted within the prior 3 years: (a) has not had a hysterectomy or (b) has had a hysterectomy and has a history of cervical intraepithelial neoplasia grade 2+ (CIN2+) in the past 20 years.

Note: If a Pap smear is conducted at V0, the results are not required prior to enrollment.

6. Have a negative urine pregnancy test at V0, if of childbearing potential;
7. Must be of non-childbearing potential\* OR must be using an effective method of birth control\*\* and must be willing to continue the method through the end of IP administration.

\*Defined as post-menopausal, or status post bilateral tubal ligation, or status post bilateral oophorectomy or status post hysterectomy.

\*\*Acceptable methods are defined as:

- a. IUDs or hormonal contraceptives for at least 22 days prior to screening. Note: Intravaginal contraceptive rings (e.g., NuvaRing) are not acceptable forms of birth control for this study.
- b. Consistent use of a barrier method, including diaphragms or condoms, for at least 13 days prior to screening.
- c. Abstinence from vaginal sexual intercourse for at least 13 days prior to screening.
- d. Exclusively same-sex relationship.
- e. Monogamous relationship with vasectomized partner.

8. Willing and able to cooperate to the extent and degree required by this protocol at the discretion of the investigator.

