**5.1.2.1 Screening Visit(s) Exclusion Criteria:**

1. Diagnosis of another vaginal or vulvar condition that may confuse interpretation of response to IP\*;  
\*For example: erosive lichen planus, desquamative inflammatory vaginitis, or contact dermatitis involving the vulvar epithelium.
2. Concurrent VVC infection with inability to be treated with oral fluconazole;
3. Infectious cause of cervicitis (e.g., *N. gonorrhoeae*, *C. trachomatis*, or *T. vaginalis*) confirmed on physical examination and/or with laboratory testing\*\*+;  
\*\* Women may be rescreened for eligibility following successful treatment of confounding STI.  
+Results of NAAT testing will be reviewed prior to enrollment.
4. Active genital lesions, including ulcers or vesicles consistent with herpes or warts;
5. Planned ongoing immunosuppressive therapy or systemic antibiotic treatment during the course of the study;
6. History of hypersensitivity, allergy or other contraindication(s) to metronidazole or other CDC-recommended BV treatment used to treat subject;
7. History of hypersensitivity to any TOL-463 formulation components (see IB for product information);
8. Current or untreated cervical intraepithelial neoplasia (CIN) or cervical carcinoma;
9. Currently pregnant or nursing;
10. Any other condition that, in the opinion of the investigator, would interfere with participation in the study;
11. Previous enrollment in the study or at the investigator's discretion.

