## 6.2 Visit 1 (Day 1) Enrollment

- Study personnel will review screening study eligibility criteria to ensure unchanged since the initial screening visit.
- Vaginal symptoms such as odor, itching, irritation, and discharge will be reviewed with the participant.
- Vulvovaginal signs such as erythema, edema, excoriation, and discharge, will be documented and graded by severity, as applicable.
- A pelvic examination to include examination of external genitalia will be conducted using a non-lubricated speculum and swabs and samples obtained for analysis of Amsel criteria; KOH and saline microscopy for identification of yeast forms, trichomonas, and clue cells. Instructions for obtaining vaginal swab specimens for these assessments are outlined in the protocol specific MOP.

---

- A clinical determination to confirm BV cure, determined by  $\leq 2$  of 4 Amsel criteria and absence of BV symptoms, are considered eligible for study enrollment. Participants who do not clear BV will be informed that they are no longer eligible. Participants who are BV cured with a secondary VVC infection but appropriate candidates for oral fluconazole treatment can be enrolled. Treatment with oral fluconazole will be per clinic standard of care and provided at no cost to the participant.
- Participants who no longer have BV, will be asked to read and sign the EIC at this time. The EIC form will be signed prior to performing any study procedures.
- Enrollment eligibility criteria will be reviewed with the participant.
- Medical history will be reviewed and updated as appropriate.
- Interim sexual history since the last clinic visit will be collected.
- A urine pregnancy test will be performed on all participants of childbearing potential and must be negative.
- All concomitant medications taken since V0 will be recorded on the appropriate DCF. Previously recorded medications will be updated as appropriate.
- Participants will be registered in Advantage eClinical after being classified as negative for BV and eligible for the study, and randomly assigned to active treatment (TOL-463 Insert) or placebo.
- A targeted physical examination including height and weight will be performed by a qualified study clinician.
- Collect vaginal swabs for Gram staining for Nugent scoring; the BD Max test; and for future analysis, for participants who consented to future use of their specimens. See the protocol-specific MOP for guidance on swab collection.

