#### 8.1.1.1 Adverse Events Grading

FDA defines an AE as any untoward medical occurrence associated with the use of a drug in humans, whether or not considered drug-related. All AEs (laboratory and clinical symptoms) will be graded for severity and assessed for relationship to IP (see definitions). AEs characterized as intermittent require documentation of onset and duration of each episode. The start and stop date of each reported AE will be recorded on the appropriate DCF and electronic case report form,

---

(eCRF). Changes in the severity of an AE will be documented to allow an assessment of the duration of the event at each level of intensity.

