**Severity of Event:**

All AEs will be assessed by the clinician using a protocol-defined grading system (refer to [Appendix B](#)). For events not included in the protocol-defined grading system, the following guidelines will be used to quantify severity:

- **Mild (Grade 1):** Events that are usually transient and may require only minimal or no treatment and generally do not interfere with the participant's daily activities.
- **Moderate (Grade 2):** Events that are usually alleviated with additional specific therapeutic intervention. The event interferes with usual activities of daily living, causing discomfort but poses no significant or permanent risk of harm to the research participant.
- **Severe (Grade 3):** Events interrupt usual activities of daily living, or significantly affects clinical status, or may require intensive therapeutic intervention. Severe events are usually incapacitating.

Changes in the severity of an AE should be documented to allow an assessment of the duration of the event at each level of intensity to be performed. AEs characterized as intermittent require documentation of onset and duration of each episode.

**Relationship to Study Products:** The clinician's assessment of the AE's relationship to IP will be done by those with the training and authority to make an assessment, or his/her designee, and the assessment will be part of the documentation process. Whether the AE is related or not, is not a factor in determining what is or is not reported in this trial. If there is any doubt as to whether a clinical observation is an AE, the event should be reported.

In a clinical trial, the study medication must always be suspect. The relationship to study medication will be assessed for AEs using the terms related or not related:

- **Related** – There is a reasonable possibility that the study product caused the AE. Reasonable possibility means that there is evidence to suggest a causal relationship between the study medication and the AE.
- **Not Related** – There is not a reasonable possibility that the administration of the study medication caused the event.

---

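### The AE baseline is set at screening, before induction treatment, and the plan leaves open whether a local symptom that clears by Visit 1 and returns on the insert is an AE

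*Protocol*

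**What the plan says.** The rule stands in Protocol 8.1.1 and is repeated in SAP 4.5.2.1: a medical condition "present at the time that the participant is screened will be considered as baseline and not reported as an AE". The next sentence reads: "However, if it deteriorates at any time during the study, it should be recorded as an AE." Neither document says whether deterioration is judged against V0 or V1.

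Screening takes place on Day -15 to -8. The inclusion criterion in Protocol 5.1.1.1 is "Women with a current BV infection and a history of at least two previous episodes of BV". VVC excludes a woman only if there is "Concurrent VVC infection with inability to be treated with oral fluconazole" (Protocol 5.1.2.1). Odor, itching, irritation and discharge are reviewed at that visit (Protocol 6.1).

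Induction treatment comes next. To be enrolled at V1 a woman must be clear of BV by Amsel criteria and free of BV discharge and odor (Protocol 5.1.1.2). Itching and irritation need not have cleared. The symptom review is repeated at V1, and the signs are recorded again: "Vulvovaginal signs such as erythema, edema, excoriation, and discharge, will be documented and graded by severity, as applicable" (Protocol 6.2).

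AEs are assessed from the IP dose through V4 (Protocol 8.1). The most common related AEs seen so far with the product were "localized in nature, e.g., vulvovaginal burning and pruritus" (Protocol 2.3.1.1).

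**The concern.** A safety baseline should describe the woman as she was just before exposure. Here it describes her with active disease, before a treatment course meant to remove that disease. The symptoms most likely to be present at V0 overlap with the product's known local reactions, so the events the trial most needs to count are the ones a screening baseline can hide.

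The measure exposed is secondary endpoint 4, product-related AEs. SAP 9.3 and Table 27 report it as a proportion per arm and a difference with a Newcombe interval. If sites leave returning symptoms unreported, both proportions fall and the difference moves toward zero. If sites read the deterioration sentence differently, part of the variation in AE rates between sites will come from wording.

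**Working it through.** The plan states no figure on this point, so there is nothing to reproduce. The check is a comparison of sections, followed by an illustration on assumed inputs.

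**1. Which visit is the reference?**

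| Item | Reference state | Place |
|---|---|---|
| What counts as an AE | Screening (V0) | Protocol 8.1.1; SAP 4.5.2.1 |
| AE collection window | From the IP dose | Protocol 8.1; SAP 4.5.2 |
| Resolution of an AE | Pretreatment status | Protocol 8.4 |
| Secondary VVC | Visit 1 | SAP Table 36, footnote a |
| Change in vaginal pH | Visit 1 | SAP Table 11 |

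Protocol 7.1 also says that examinations from V1 onward look for treatment-emergent AEs, but neither document defines that term. Nothing resets the AE baseline to V1.

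**2. What the rule does in practice.** Take itching, which Appendix B grades 1 or 2:

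| V0 | V1 | On insert | Judged against V0 | Judged against V1 |
|---|---|---|---|---|
| 1 | 0 | 1 | Baseline | AE |
| 2 | 1 | 2 | Baseline | AE |
| 1 | 0 | 2 | AE | AE |
| 0 | 0 | 1 | AE | AE |
| 2 | 2 | 2 | Baseline | Baseline |

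The readings differ only in the first two rows: the symptom improved by V1 and came back at no more than its V0 level. The text supports either reading of those rows.

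**3. How large could the loss be?** Let s be the share of related AEs left unreported for this reason, taken as equal in both arms. Then observed proportion = true proportion × (1 − s), and observed difference = true difference × (1 − s). The ratio of proportions would not change, but the SAP tabulates the difference.

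Inputs: 125 per arm (planned enrollment). The true proportions and s are assumptions; the documents give neither. The Newcombe limits are d − √[(p1 − l1)² + (u2 − p2)²] and d + √[(u1 − p1)² + (p2 − l2)²], where l and u are the Wilson limits of each arm. At 20% v 10% and s = 0 the Wilson limits are 13.9% to 27.9% and 5.9% to 16.5%. The lower limit is 0.10 − √(0.061² + 0.065²) = 0.011, and the upper is 0.10 + √(0.079² + 0.041²) = 0.189.

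| s | True 20% v 10%: observed difference, points (95% CI) | True 30% v 15%: observed difference, points (95% CI) |
|---|---|---|
| 0 | 10 (1.1 to 18.9) | 15 (4.7 to 25.0) |
| 10% | 9 (0.5 to 17.6) | 13.5 (3.5 to 23.2) |
| 30% | 7 (−0.7 to 14.9) | 10.5 (1.4 to 19.5) |
| 50% | 5 (−1.7 to 12.0) | 7.5 (−0.4 to 15.6) |

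The intervals are evaluated at the expected proportions. SAP section 5 says the study closed early; with smaller arms they would be wider.

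The ceiling on s is the share of local reactions that occur in women who had the same symptom at V0. It is reached only if all of those symptoms return at no more than their V0 level and every site applies the rule literally. Equal s is also an assumption. Randomization balances V0 symptoms on average, but not necessarily the share of reactions that fall in women who had them.

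**The case against.** The strongest reply is that the plan does not order sites to discard these events. A woman with no itching at V1 who itches after dosing has, in ordinary language, deteriorated during the study. Protocol 8.1.1.1 adds a tie-break: "If there is any doubt as to whether a clinical observation is an AE, the event should be reported". This stands, and it rules out the stronger inference a reader might draw, that every returning symptom must go unreported. It does not settle the matter. Screening is the only baseline the rule names, and a site that applies the sentence as written may see no doubt to resolve. The provision that "AEs characterized as intermittent require documentation of onset and duration of each episode" helps only once an event has been accepted as an AE.

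A reader might also infer that returning VVC is lost. It is not: culture-confirmed VVC after the start of treatment is its own secondary endpoint in the Safety Population, and Table 36 takes V1 as baseline. Only its entry as an AE is exposed.

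Nor do local symptoms vanish from the report. Table 37 shows burning, irritation, itching, edema, erythema and excoriation by severity, visit and arm. It is a partial substitute, because it carries no onset date or relatedness judgment, and scheduled visits are about four weeks apart.

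A reader might infer that the halting rules are blunted. The effect on the numeric Grade 3 rule is small: Appendix B gives no Grade 3 for itching or Candida, and an event that reaches Grade 3 from a lower screening grade is a deterioration on any reading. The judgment-based pattern rule is the more plausible exposure.

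**Conclusion.** The point holds in limited form. The AE baseline is placed before induction treatment, and the return of a condition that cleared by V1 is not addressed. The affected events overlap with the product's known local reactions. Table 27 is therefore open to under-counting in both arms and to differences between sites; if suppression is equal across arms, the difference shrinks by the factor (1 − s).

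The size is unknown, from near zero up to the ceiling given above. A reader might take the larger losses in the illustration as expected values, or conclude that the product will look safer than it is. The documents support neither: they give no symptom frequency at V0, no local reaction rate and no evidence of how sites applied the rule. This is a cheap improvement that should be made.

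**What to change.** In Protocol 8.1.1 and SAP 4.5.2.1, define the AE baseline as status at V1 before the first IP dose. A condition absent at V1 that appears after dosing, or one that is worse than at V1, is recorded as an AE even if it was present at V0. State that recurrent BV is captured as the efficacy endpoint.

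Because the study has closed, the wording change cannot recover events already left unreported. For the data in hand:

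- Add to the SAP a by-arm summary, in the Safety Population, of women whose burning, itching, irritation, edema, erythema or excoriation at V2 to V4 or early termination is new or worse than at V1.
- Take the V1 value from the V1 record itself. Table 37 folds early-termination findings into the preceding scheduled visit at maximum severity. For a woman who leaves at an unscheduled visit before V2, this would put an on-treatment symptom in the V1 column.
- Disclose with Table 27 that AEs were collected against a screening baseline.

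The cost is a short wording change in each document, one extra table from data already collected, and somewhat higher AE counts wherever the new definition is applied. No visit or procedure is added. The extra table has no relatedness judgment and cannot restore events missing from Table 27.
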